4.2.2. Procedure related

4. Serious unresolved periprocedural complications

4.2.3. Medication related

5. Any contraindication to EITHER Edoxaban OR VKA per local label; this includes hypersensitivity to the active ingredient, or to any of the excipients, or any of the components of the study medications
6. Concomitant treatment with other antithrombotic agents, ASA > 100 mg/day, fibrinolytic therapy, or chronic (> 4 days/week) use of nonsteroidal anti-inflammatory drugs (NSAIDs); however, NSAID patches are permitted
7. Requirement for DAPT at randomization that will be indicated for more than 3 months beyond the first study dose of OAC
8. Treatment with other investigational (i.e., non-approved) drugs or devices within 30 days before enrollment or planned use of investigational drugs or devices during the study

4.2.4. Concomitant conditions and therapies

9. Clinically overt stroke within the last 90 days before TAVI
10. Any scheduled drug or device-based therapy during the treatment period that would eliminate the need for chronic oral anticoagulation (any other diagnostic or therapeutic procedure that is associated with temporary interruption of OAC is permitted)
11. *(former exclusion criteria 11 is no longer applicable, numbers not adjusted to keep alignment with version 2.0 of the protocol)*
12. Any bail out catheter based cardiac interventional procedure during the index TAVI (however, during the same session as TAVI (pre or post TAVI) scheduled PCI and angioplasty of the iliac/femoral arteries are permitted)
13. Subjects with mechanical heart valves
14. Mitral valve stenosis Grade III-IV/IV (moderate to severe/severe); however, subjects with moderate mitral valve stenosis may be enrolled into the study
15. Active infective endocarditis
16. Major surgery within 30 days prior to randomization
17. *(former exclusion criteria 17 is no longer applicable, numbers not adjusted to keep alignment with version 2.0 of the protocol)*
18. ST-elevation myocardial infarction within 30 days prior to TAVI until randomization (non-ST-elevation myocardial infarction is no exclusion)

19. End stage renal disease (creatinine clearance [CrCL] < 15 mL/min or dialysis) at randomization
20. Severe hepatic impairment or hepatic disease associated with coagulopathy (e.g., acute/chronic active hepatitis or cirrhosis, Child Pugh B, C)
21. Uncontrolled severe hypertension documented by repeated BP \geq 170/100 mmHg, despite medical intervention
22. Respiratory failure requiring mechanical ventilation at time of randomization
23. Critically ill or hemodynamically unstable subjects at the time of randomization, i.e., cardiogenic shock, acute heart failure, including the requirement for pharmacologic treatment or mechanical support to assist circulation
24. Active malignancy (requiring chemotherapy, radiation or surgery at the time of randomization) except for adequately treated non-melanoma skin cancer or other noninvasive or in situ neoplasms (e.g., cervical cancer in situ that has been successfully treated); anti-hormonal therapy is allowed

4.2.5. Other exclusion criteria

25. Any of the following abnormal local laboratory results at the time of randomization:
 - Platelet count < 50 x 10⁹/L
 - Hemoglobin < 8 g/dL (5 mmol/L at randomization, no ongoing bleeding, no transfusion of whole blood or red blood cells within 24 hours); however, for subjects with a history of hemoglobin of no less than 7.5 g/dL while under chronic OAC, the exclusion will be based on hemoglobin of <7.5 g/dL
26. Female subjects of childbearing potential without using highly effective methods of contraception (i.e., a method of contraception with a failure rate < 1% during the course of the study, including the follow-up period). A female of childbearing potential is defined as one who has not been postmenopausal for at least one year, or has not been surgically sterilized, or has not had a hysterectomy at least three months prior to the start of this study [Visit 1]). Females taking oral contraceptives should have been on that therapy for at least three months. Highly effective methods of contraception includes combined (estrogen and progestogen containing) oral, intravaginal or transdermal hormonal contraception associated with inhibition of ovulation; progestogen-only oral, injectable or implantable hormonal contraception associated with inhibition of ovulation; intrauterine device (IUD); intrauterine hormone-releasing system (IUS); bilateral tubal occlusion; vasectomized partner; along with barrier methods of contraception (male condom, female condom, cervical cap, diaphragm, contraceptive sponge).
27. Pregnant or breast-feeding subjects
28. Assessment by the Investigator that the subject is not likely to comply with the study procedures or will complete follow-up
29. Current participation in another clinical trial (unless the registry DOES NOT interfere with the evaluation of ENVISAGE-TAVI-AF as per this protocol.

Before including such a subject, the Investigator should discuss the situation with the Daiichi Sankyo Medical Lead or his/her designee)

30. Previous randomization in this study
31. Drug or alcohol dependence within the past 12 months prior to randomization as judged by the Investigator
32. Life expectancy less than 6 months beyond the targeted last visit
33. Subjects with antiphospholipid syndrome who are triple positive (for lupus anticoagulant, anticardiolipin antibodies, and anti-beta 2-glycoprotein I antibodies) with thrombosis

5. STUDY TREATMENT(S)

5.1. Assigning Subjects to Treatments and Blinding

5.1.1. Treatment Group(s)

Following the signing of written informed consent, subjects are screened for eligibility and may be randomized the evening of the day of TAVI to 5* days, i.e., until 23:59 of the 5th* day after the successful TAVI (see inclusion criteria #1 for definition of “successful”) and the subject is qualified based on all the protocol defined inclusion/exclusion criteria. The first dose of OAC should be administered within the 5 days after TAVI (in case of pacemaker deployment within the 7days after TAVI) but must be administered within 24 hours post randomization; however, NO EARLIER than the morning after successful TAVI. Low-dose aspirin treatment (75-100 mg/day) or approved other P2Y₁₂ antagonist, preferably clopidogrel (75 mg/day), will be prescribed as per Investigator discretion. This needs to be pre-declared prior to randomization. Treatment duration will be as per the protocol for up to 36 months (with a minimum of 6 months for last subject enrolled) unless the subject reaches a primary endpoint. However, the subject will continue to be followed until the end of the study (i.e., this may be longer than to end of treatment).

*If subject is waiting on a decision on pacemaker surgery, then can extend to 7 (7th) days

Treatment arms include:

- **Treatment arm 1 [Experimental]: Edoxaban** – 60 mg once-daily or 30 mg once-daily in subjects meeting the dose reduction criteria per the locally approved label.
- **Treatment arm 2 [Control]: VKA** – The oral VKA of choice (any locally approved) dose-adjusted throughout the study to obtain an INR of 2.0 to 3.0 (numbers inclusive) [Japan: 1.6 to 2.6 in subjects aged ≥ 70 (numbers inclusive)].

In addition to the above described oral anticoagulation therapy, antiplatelet management in this study shall follow the scenarios as outlined below:

- Subjects having undergone TAVI without other potential indications for APT may obtain either no APT or SAPT up to 90 days, i.e., ASA or a P2Y₁₂ inhibitor (preferably clopidogrel).
- Subjects having undergone TAVI with PCI either prior to or during the study period may obtain SAPT indefinitely, i.e., any P2Y₁₂ inhibitor (preferably clopidogrel) or ASA. Dual antiplatelet therapy (DAPT) is only allowed post stenting for up to 3 months after each PCI during the study period.
- Subjects having undergone TAVI with other potential indications for oral antiplatelet therapy may obtain either no APT or SAPT, i.e., any P2Y₁₂ inhibitor (preferably clopidogrel) or ASA indefinitely.

The type (i.e., the international nonproprietary name, the dose, and the projected last dose of all antiplatelet agents) must be predeclared at randomization. ASA 75-100 mg/day or generic/branded clopidogrel 75 mg/day (chronic therapy following loading dose) are the preferred agents. Type, dose, and (projected) last dose may be changed during the treatment period for documented medical reasons.

5.1.2. Method of Treatment Allocation

Prior to randomization of a subject, all eligibility criteria must be met and a signed informed consent obtained.

Enrollment and randomization must occur between the evening of the day of TAVI and 5* days, i.e., until 23:59 of the 5th* day provided that the TAVI procedure has been judged as successful (See inclusion criteria #1 for definition of successful TAVI) and the subject is qualified based on all the protocol defined inclusion/exclusion criteria. All sites will be required to maintain a record of all subjects screened for the trial. The reason for screen failure must be documented in the subject's records. Subjects must be randomized without delay and administered their first dose of study medication within 24 hours post randomization; however, NO EARLIER than the morning after successful TAVI. Randomization will be performed using the IXRS system for subjects meeting all eligibility criteria. The directions on how to use the system will be provided in the IXRS Quick Reference Manual. The randomization scheme will be securely stored at the statistical department of the database management center.

*If subject is waiting on a decision on pacemaker surgery, then can extend to 7 (7th) days

Based on this information, the system will assign a unique subject identification number and treatment for that subject. Trial randomization will not be blinded and once subject is assigned to a treatment arm, no treatment cross-over is permitted. Subjects will be randomly assigned in a 1:1 ratio to receive Edoxaban or VKA. The Investigator will pre-declare the type (if any) P2Y₁₂ antagonist or ASA treatment and its projected last dose prior to the randomization (pre-declaration, via the IXRS).

The Investigator's knowledge of the treatment must not influence the decision to enroll a particular subject or affect the order in which subjects are enrolled.

5.1.3. Blinding

This study is open-label.

5.2. Study Drug(s)

5.2.1. Description

The primary medications within this study are Edoxaban and VKA, referred to as study medications. The oral antiplatelet (OAP) co-administered medications for the purpose of this protocol are not referred to as study medications, but are within the term study drugs. The costs of OAP and VKA for this study will be reimbursed.

5.2.1.1. Edoxaban:

60 mg and 30 mg film-coated tablets for once-daily oral use and 15 mg film-coated tablets for transitioning at end of treatment. Dosing must follow the locally approved label.

5.2.1.1.1. Transitioning from Other Anticoagulants to Edoxaban at Randomization

For subjects randomized to the Edoxaban-based regimen that require switching from another anticoagulant the following algorithm should be used. Capture the date and timing of first study dose in the electronic case report form (eCRF).

Table 5.1: Transitioning to Edoxaban at Randomization

Switching to edoxaban		
From	To	Recommendation
VKA	edoxaban	Discontinue the VKA and start edoxaban when INR is ≤ 2.5 .
Other non-VKA OAC drugs • dabigatran • rivaroxaban • apixaban	edoxaban	Discontinue the OAC and start edoxaban at the time of the next OAC dose.
Parenteral anticoagulants	edoxaban	These agents should not be administered simultaneously. Subcutaneous anticoagulant (i.e. LMWH, fondaparinux): discontinue subcutaneous anticoagulant and start edoxaban at the time of the next scheduled subcutaneous anticoagulant dose. Intravenous unfractionated heparin: Discontinue the infusion and start edoxaban 4 hours later.

INR = international normalized ratio; OAC = Oral anticoagulant(s); VKA = vitamin K antagonist

5.2.1.1.2. Transition from Edoxaban at EOT

For subjects randomized to the Edoxaban-based regimen that require switching from Edoxaban to another anticoagulant at the scheduled end of treatment (EOT) (or due to a premature Edoxaban discontinuation) the following algorithm should be used:

Table 5.2: Transitioning from Edoxaban at EOT

Switching from Edoxaban		
From	To	Recommendation
Edoxaban	VKA	During the transition from Edoxaban to VKA, continuous adequate anticoagulation should be ensured during any transition to an alternate anticoagulant. Oral option: 
 For subjects currently on a 60 mg once-daily dose, administer an Edoxaban dose of 30 mg once-daily together with an appropriate VKA dose. For subjects currently on a 30 mg dose once-daily (for one or more of the following factors: moderate to severe renal impairment (CrCL = 15 to ≤ 50 mL/min), low body weight, or use with certain

Switching from Edoxaban		
From	To	Recommendation
		
P-gp inhibitors), administer an Edoxaban dose of 15 mg once-daily together with an appropriate VKA dose. Edoxaban 15 mg once-daily is not indicated as monotherapy, as it may result in decreased efficacy. It is only indicated in the process of switching from Edoxaban 30 mg once-daily to VKA, together with an appropriate VKA dose.
 
Subjects should not take a loading dose of VKA in order to promptly achieve a stable INR of 2.0 to 3.0 (numbers inclusive) [Japan: 1.6-2.6 in subjects aged ≥ 70 (numbers inclusive)]. It is recommended to take into account the maintenance dose of VKA if the subject was previously taking a VKA or to use valid INR driven VKA treatment algorithm, in accordance with local practice.
 
Once an INR ≥ 2.0 is achieved [Japan: ≥ 1.6 in subjects aged ≥ 70], Edoxaban should be discontinued. Most subjects (85%) should be able to achieve an INR ≥ 2.0 [Japan: 1.6 in subjects aged ≥ 70 (numbers inclusive)] within 14 days of concomitant administration of Edoxaban and VKA. After 14 days it is recommended that Edoxaban is discontinued and the VKA continued to be titrated to achieve an INR of 2.0-3.0 (numbers inclusive) [Japan: 1.6-2.6 in subjects aged ≥ 70 (numbers inclusive)]. It is recommended that during the first 14 days of concomitant therapy the INR is measured at least three times just prior to taking the daily dose of Edoxaban to minimize the influence of Edoxaban on INR measurements. Concomitant Edoxaban and VKA can increase the INR post Edoxaban dose by up to 46%.
 
Parenteral option: Discontinue Edoxaban and administer a parenteral anticoagulant and VKA at the time of the next scheduled Edoxaban dose. Once a stable INR of ≥ 2.0 is achieved [Japan: ≥ 1.6 in subjects aged ≥ 70], the parenteral anticoagulant should be discontinued and the VKA continued.

Edoxaban	Other non-VKA OAC drugs	Discontinue Edoxaban and start the non-VKA anticoagulant at the time of the next scheduled dose of Edoxaban.
Edoxaban	Parenteral anticoagulants	These agents should not be administered simultaneously. Discontinue Edoxaban and start the parenteral anticoagulant at the time of the next scheduled dose of Edoxaban.

CrCL = creatinine clearance; INR = international normalized ratio; OAC = Oral anticoagulant(s);
P-gp = P-glycoprotein; VKA = vitamin K antagonist

5.2.1.2. VKA

Any oral VKA tablet of choice for use in accordance with the local label to obtain an INR of 2.0 to 3.0 (numbers inclusive) [Japan: 1.6 to 2.6 in subjects aged ≥ 70 (numbers inclusive)]

It is the responsibility of the Investigator to collect INR at study visits, and in between study visits (preferably monthly), as needed per standard of care, in order to maintain INR within the target range. The Investigator will monitor the INR and adjust the VKA dose to maintain the INR within target (2.0 to 3.0 (numbers inclusive) [Japan: 1.6-2.6 in subjects aged ≥ 70 (numbers inclusive)]), unless performed by the subject's treating physician. The Investigator will record any changes in VKA dosage within the eCRF.

5.2.1.2.1. Transitioning to Study VKA at Randomization

For subjects randomized to VKA, who require switching from any other anticoagulant i.e., another VKA, other non-VKA OAC, or parenteral anticoagulants, follow the guidance for switching in the locally approved labels of these products. Capture the date and timing of first study dose in eCRF.

Table 5.3: Transitioning to Study VKA at Randomization

Switching to VKA		
From	To	Recommendation
Vitamin K Antagonist (VKA)	Study VKA	If the INR measured on the day of randomization is: 
 • ≤ 2.5, start study VKA • > 2.5, the Investigator or designee must recheck at a later time; start study VKA when the INR is ≤ 2.5; document the INR value and the date it was measured.
Other non-VKA OAC drugs 
 • dabigatran • rivaroxaban • apixaban 	Study VKA	Ascertain adequate anticoagulation until an INR ≥ 2.0 is reached and then continue with study VKA only. Follow local label of country-selected VKA and label of NOAC being stopped for further guidance.
Parenteral anticoagulants	Study VKA	For subjects not previously on VKA, bridging with parenteral anticoagulation is permissible, but not recommended. For initiation of VKA therapy and related bridging with parenteral anticoagulation, follow locally established guidelines and local approved label (prescribing information) from the VKA manufacturer.

INR = international normalized ratio; NOAC = non- oral anticoagulant(s); OAC = oral anticoagulant(s); VKA = vitamin K antagonist

5.2.1.2.2. Transitioning from Study VKA at EOT**Table 5.4: Transitioning from Study VKA at EOT**

Switching from VKA		
From	To	Recommendation
Study VKA	VKA	When transitioning a subject to post-study VKA, either maintain the subject on the same maintenance dose or adjust the dose of VKA to maintain an INR between 2.0-3.0 and follow the local guidelines for managing patients on VKA therapy.
Study VKA	Other non-VKA OAC drugs	When transitioning a subject to a newer non-VKA oral anticoagulant, switching guidance in the locally approved label of the non-VKA anticoagulant should be followed.

INR = international normalized ratio; OAC = Oral anticoagulant(s); VKA = vitamin K antagonist

5.2.1.3. P2Y₁₂ antagonist:

Clopidogrel (generic/branded) 75 mg, commercially/locally available tablets for once-daily oral use is the preferred P2Y₁₂ antagonist for this study.

5.2.1.4. Acetylsalicylic acid (ASA):

ASA 75-100 mg once-daily for oral use.

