Following signing of written informed consent, subjects are screened for eligibility and may be randomized from the evening of the day of TAVI to 5* days, i.e., until 23:59 of the 5th* day after the successful TAVI procedure (see inclusion criteria #1 for definition of “successful”) and the subject is qualified based on all the protocol-defined inclusion/exclusion criteria. The first dose of OAC should be administered within the 5 days after TAVI (in case of pacemaker deployment within the 7 days after TAVI) but must be administered within 24 hours post randomization, however NO EARLIER than the morning after successful TAVI.

*If subject is waiting on a decision on pacemaker surgery, then can extend to 7 (7th) days

Subjects eligible to participate in the study will be randomized via interactive web/voice response system (IXRS) such that the study will have a 1:1 ratio of subjects in the following study arms:

- **Edoxaban-based regimen:**
 - Edoxaban 60 mg once-daily or 30 mg once-daily in subjects meeting the dose reduction criteria per locally approved label

 - **VKA-based regimen:**
 - The VKA of choice (any locally approved), dose-adjusted throughout the study to achieve an international normalized ratio (INR) of 2.0 to 3.0 (numbers inclusive)
-

[Japan: 1.6 to 2.6 in subjects aged ≥ 70
(numbers inclusive)].

In addition to the above described oral anticoagulation therapy, antiplatelet management in this study shall follow the scenarios as outlined below:

- Subjects having undergone TAVI without other potential indications for antiplatelet therapy (APT) may obtain either no APT or single antiplatelet therapy (SAPT) up to 90 days, i.e., acetylsalicylic acid (ASA) or any P2Y₁₂ inhibitor (preferably clopidogrel).
- Subjects having undergone TAVI with percutaneous coronary intervention (PCI) either prior to or during the study period may obtain SAPT indefinitely, i.e., any P2Y₁₂ inhibitor (preferably clopidogrel) or ASA. Dual anti-platelet therapy (DAPT) is only allowed post stenting for up to 3 months after each PCI during this study.
- Subjects having undergone TAVI with other potential indications for oral antiplatelet therapy may obtain either no APT or SAPT, i.e., any P2Y₁₂ inhibitor (preferably clopidogrel) or ASA indefinitely.

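### Table 5.3 ends anticoagulant cover in the NOAC-to-VKA switch at INR ≥ 2.0 everywhere, although the Japan target at age 70 or over starts at 1.6 and Table 5.2 stops cover there

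*Combined protocol and SAP*

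**What the plan says.** Section 5.2.1.2 gives the VKA target as INR 2.0 to 3.0, with an exception: "Japan: 1.6 to 2.6 in subjects aged ≥ 70 (numbers inclusive").

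Section 5.2.1.2.1 covers the start of study VKA at randomization. Its opening sentence tells sites to "follow the guidance for switching in the locally approved labels of these products". Table 5.3 then prints, for subjects coming from dabigatran, rivaroxaban or apixaban: "Ascertain adequate anticoagulation until an INR ≥ 2.0 is reached and then continue with study VKA only". The row closes by pointing again to the local VKA and NOAC labels. It names no covering agent and prints no maximum duration.

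Table 5.2 (section 5.2.1.1.2) handles the switch from edoxaban to VKA at end of treatment. Oral route: "Once an INR ≥ 2.0 is achieved [Japan: ≥ 1.6 in subjects aged ≥ 70], Edoxaban should be discontinued". Parenteral route: "Once a stable INR of ≥ 2.0 is achieved [Japan: ≥ 1.6 in subjects aged ≥ 70], the parenteral anticoagulant should be discontinued".

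**The concern.** All three of these INR values do the same job: they say when the VKA can be trusted alone and the other anticoagulant stopped. Two carry a Japan value and one does not. The Japan range is otherwise repeated throughout the protocol wherever on-study VKA treatment is defined, and also for compliance (section 5.5) and time in therapeutic range (section 11.3). No reason is given for a higher stop value at randomization, so this reads as an omission.

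The stake is a longer overlap of two anticoagulants soon after TAVI, in older subjects for whom the protocol chose a lower INR range. Subjects without another indication for antiplatelet therapy "may obtain either no APT or single antiplatelet therapy (SAPT) up to 90 days", so the overlap may come on top of an antiplatelet agent. Major bleeding is a co-primary objective.

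**Working it through.** No statistical figure is involved. The check sets the thresholds side by side.

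| Place | General value | Japan, age ≥ 70 |
|---|---|---|
| Section 5.2.1.2, VKA target | 2.0 to 3.0 | 1.6 to 2.6 |
| Table 5.2, oral cover, stop value | ≥ 2.0 | ≥ 1.6 |
| Table 5.2, parenteral cover, stop value | ≥ 2.0 | ≥ 1.6 |
| Table 5.3, NOAC row, stop value | ≥ 2.0 | none printed |

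**Step 1: stop value minus lower limit of the subject's own target.**
- Table 5.2, general: 2.0 − 2.0 = 0. Japan, age ≥ 70: 1.6 − 1.6 = 0. Both routes agree.
- Table 5.3, general: 2.0 − 2.0 = 0. Japan, age ≥ 70: 2.0 − 1.6 = 0.4.

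The pattern is that cover stops when the lower limit is reached. Table 5.3 departs from it only for Japanese subjects aged 70 or over. An INR from 1.6 to below 2.0 counts as in range for compliance and time in range, but does not meet the printed stop value. A subject held at 1.8, say, is correctly titrated and never meets it.

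**Step 2: is there another end point?** Table 5.2's oral option recommends stopping edoxaban after 14 days regardless. The Table 5.3 row has no such limit, so INR ≥ 2.0 is the only end point it prints.

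**Step 3: can the added days be derived?** That needs the rate of INR rise, the starting INR and the testing schedule in this subgroup. The documents give none of these. Table 5.2 does expect most subjects (85%) to reach its stop value "within 14 days of concomitant administration of Edoxaban and VKA", but for Japanese subjects aged 70 or over that stop value is 1.6, not 2.0. Outside Table 5.2, INR tests between visits are as needed and preferably monthly.

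**Step 4: is 1.6 safe to copy on its own?** Table 5.2 warns that edoxaban can raise the post-dose INR by up to 46%, and recommends INR measurement just before the daily dose. If a NOAC used as cover in Table 5.3 interfered to the same degree (an assumption, since 46% is the edoxaban figure), then:
- a measured 1.6 could reflect 1.6 / 1.46 = 1.10 from the VKA;
- a measured 2.0 could reflect 2.0 / 1.46 = 1.37.

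Both lie below 1.6, so the printed rule is exposed to this too, but the lower threshold more so. The Japan value should therefore come with pre-dose sampling.

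**The case against.** The strongest reply is that local labels govern. The section opens by deferring to them, the column is headed as a recommendation, and the row ends with the same deferral. Section 5.7 also restricts other anticoagulants, with an exception for parenteral bridging under the local label. The Japanese labels may already give another threshold, and they are not in the documents. This stands as a limit on the claim. It does not remove it: the row refers to labels only after printing a number, and footnote l of Table 17.1 defers to the label at end of treatment too, where the Japan value is printed all the same.

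Second, the two switches differ. Table 5.2's oral option halves the edoxaban dose and adds a sampling rule; Table 5.3 concerns other drugs and has neither. That is a fair warning against copying the threshold alone, and the fix takes it up.

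Third, INR 2.0 lies inside 1.6 to 2.6 and need be reached only once. That also stands: the row pushes nobody out of target.

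Two stronger readings are tempting. A reader might treat 14 days as the time to reach 2.0, assume a straight-line rise, and quote several added days of cover. The documents do not support this, because for this subgroup the 14 days belong to 1.6, and the starting INR, the linear rise and daily testing would all be assumed. With sparse testing, one result may clear both thresholds and the difference is zero.

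A reader might also infer a bias against VKA, since in the edoxaban arm Table 5.1 has no overlap: "Discontinue the OAC and start edoxaban at the time of the next OAC dose". But some overlap belongs to starting a VKA whatever the threshold, and nothing in the documents sizes the part due to the missing bracket.

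**Conclusion.** The inconsistency is real and narrow. It concerns Japanese subjects aged 70 or over, randomized to VKA, who come from a NOAC. For them the printed stop value is 0.4 INR units above the lower limit of their own target, and someone in target between 1.6 and below 2.0 stays on cover with no printed time limit. This rests on a literal reading of the row and on the local label giving no other threshold. The documents do not give the number of such subjects or the extra duration of cover. Sample size, type I error, the hazard ratio and the planned analyses are untouched. It is a low-cost safety clarification to consider.

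**What to change.** In the NOAC row of Table 5.3:
- After the 2.0 threshold, insert the Japan bracket from Table 5.2 (≥ 1.6 at age 70 or over).
- At the end of that sentence, add: if a NOAC is used as cover, measure INR just before the next NOAC dose.
- Keep the sentence on local labels as it is.

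This can go into the next amendment or a letter to sites in Japan. It adds no visits, subjects or analyses. The downside is that INR draws must be timed to the NOAC dose, and cover ends slightly earlier in this subgroup.
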